17. **Objectives:** State the research hypothesis or the question that the research will answer. List the research objectives and expected outcomes. **A primary outcome or objective must be identified.** After the statement of the primary objective, secondary objectives may be listed. Objectives should be simple and specific.

Hypothesis: Patient experience and outcome after outpatient upper extremity orthopedic surgery can be improved by a formalized education program (video and handout) regarding post-operative pain management.

Primary outcome:

1. QoR-15 scores (post-operative day "POD" 2),
  - a. 15-question validated outcome measurement tool used in the setting of outpatient surgery which takes about 2.5 minutes to complete and includes pain as one of its outcome domains

Secondary Outcomes:

2. PROMIS short forms administered on POD 3 – (GI belly pain 5a, GI nausea and vomiting 4a, Pain Intensity 3a, Pain Interference 4a, Sleep Disturbance 4a, Cognitive Function 4a)
3. number of narcotic pills used – 7 days,
4. daily pain level (by 0-10 rating scale) – 7 days,
5. patient-reported satisfaction and feeling of control (4 point rating scale)
6. number of pain-related calls/visits to a healthcare provider
7. use of non-narcotic adjunct pain relief medication and modalities
8. incidence of high risk activities (combining narcotics with muscle relaxants/sedatives/alcohol, etc.; combining prn NSAIDs with regularly dosed prescription NSAIDs, exceeding daily recommended doses)
9. incidence of side effects and adverse events,
10. demonstrated patient knowledge as measured by score on the follow-up quiz, and
11. prevalence of chronic opioid use.

Positive improvements in some or all of these measurements are expected with this patient education intervention. The Quality of Recovery-15 survey is a 15-question validated outcome measurement tool used in the setting of outpatient surgery which takes about 2.5 minutes to complete and includes pain as one of its outcome domains

18. **Study Design:** Give a description of the research design including use of placebo, randomization and an explanation of what is experimental. Include type of study: descriptive, retrospective, cross-sectional, longitudinal, prospective observational, pilot, experimental (controlled or non-controlled) or pilot.

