#### Exclusion criteria will include:

1. Patients unable or unwilling to provide informed consent
2. Patients unable to unwilling to participate in the trial (poor English language skills, blindness, cognitively disadvantaged, poor literacy skills, other barriers to participation)
3. Patients who are or suspect they may be pregnant.
4. Patients for whom the medical provider, in his professional judgment, does not feel that the study protocol would be appropriate. (to be tracked)

Inclusion and exclusion criteria were selected by the PI with the intention to make the study population as inclusive as possible to represent since the goal of the videos is to have them available

for general patient viewing. Pediatric patients and pregnant patients are excluded as these represent populations with special ethical and medical considerations (such as drug dosing, medication effect on the fetus) which are not addressed in this study. Also, the educational program is designed for adult learners.

20. **Methodology:** List all activities or procedures that will be performed (pre-treatment tests and medications, tests and medications used during therapy, diagnostic tests, x-rays, lab tests, questionnaires and other forms, interviews, chart reviews etc.) Describe how, when and where research activities will be administered and analyzed. **Distinguish any standard processes from those that are research.** Please describe activities/procedures in a step-by-step chronological order. State the length of time subjects will be in the study and the expected amount of time required for each study visit or activity.

1. Recruitment – 10 minutes

A desk-top sign advertising the study will be displayed in patient rooms used by the Hand Section providers for patient visits.

All patients who are consented or scheduled for surgery during a clinic visit with a Hand Section provider at the ION building (when a designated enrollment investigator is present/available) will be considered for the study. These patients will be referred to the designated enrollment investigator, who will present the participation opportunity to the patient after the conclusion of the visit with the provider. The designated enrollment investigator may be a study coordinator, medical student, or other investigator, but will not be the treating physician. Study coordinators will be utilized in this role whenever possible, although scheduling and budget restraints will make mixed coverage necessary.

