    - a. A series of two 6-minute videos. The first video, Managing Pain after Outpatient Surgery, Part 1, discusses a tiered approach to pain management, including rest, ice, elevation, distraction, and medication. Three classes of pain medication commonly used after surgery, including nonsteroidal anti-inflammatories, acetaminophen, and opioids, are discussed, including the role of each medication and the risks and side effects. Naloxone, an antidote to opioid medication for emergency use, is introduced. The second video, Managing Pain after Outpatient Orthopedic Surgery, Part 2, instructs the patient on how to make a Pain Plan with regard to post-operative pain medication, including the use of over the counter pain medications and a medication diary. (12 minutes)
    - b. Recovery Medication Diary (1-7 minutes, daily, for 7 days)
  - 2) Wound Care Education (Control)
    - a. A single video, Caring for Your Closed Wound, discusses the types of sutures that are used to close surgical wounds, the specifics of wound care and dressing changes, swelling management, restriction of physical activity, scarring of the surgical site and

methods to reduce scarring, and guidance on when to call their physician if they suspect something to be wrong following their procedure. (6 minutes)

Patients are encouraged to view the video(s) in the examining room of the clinic before departure on a tablet device. Patients who elect to watch the video will be offered a small bottle of water, due to the extended visit and as a “fidget” to aid in attention. The videos will also be “assigned” to the patient in MyChart through the GetWellNetwork, and also available for viewing online on the Carilion channel on YouTube.

5. Patient packet dissemination (< 1 minute)

All patients in the study will receive an enrollment package with includes a copy of the consent form, video web address, and Patient Education Diary (experimental or placebo version). Patients in the Pain Control Video group will also receive a Recovery Diary corresponding to the video.

6. Data Collection (1-7 minutes daily for 7 days)

Patients are invited to view the video on the GetWellNetwork through MyChart and on YouTube. Viewing will be tracked by patient report, and by tracking views on the GetWellNetwork. (Viewing by patient report will be used in statistical analysis, comparison to GetWellNetwork data will be exploratory.)

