**Outcome Measure Data:**

1. QoR-15 scores (primary outcome),
2. Selected short form PROMIS questionnaires,
3. number of narcotic pills used,
4. daily pain level (by 0-10 rating scale) for days 0-7,
5. patient-reported satisfaction and feeling of control (10 point rating scale),
6. calls/visits to a health care provider for pain or related concerns
7. use of non-narcotic adjunct pain relief medications and modalities,
8. incidence of side effects and adverse events
9. reported frequency of noting pain medication dose times,
10. demonstrated patient knowledge as measured by score on the follow-up quiz, and prevalence of chronic pain, long term narcotic and non-narcotic pain medication use.

Data will be collected by chart review (for demographic data and data pertaining to the surgery, anaesthetic, and initial narcotic prescription), physician and patient reporting, and by patient diary/surveys (which will be completed by the patient at home and returned at the follow-up visit or by mail). Follow-up phone calls will act as a reminder to help encourage completion of the study. Information regarding how many times a video was viewed will be collected by patient questionnaire (measured outcome to be used in analysis), reviewing Mychart data, and counting Youtube hits.

22. **Statistical Analysis:** State how qualitative and/or quantitative data will be analyzed. This must include a statement from a statistician that there is sufficient power to determine the primary study outcome or objective. Other outcomes may be listed as secondary and descriptive. If this is a proof of concept or feasibility study that includes limited efficacy testing, there must be a statistician statement that the appropriate design is in place to determine whether an intervention should be recommended for broader efficacy testing. If a study is meant to be solely descriptive, then results apply only to the sample being studied and conclusions cannot be drawn about the larger population; therefore, the primary outcome or objective must be limited in scope.

Standard descriptive statistics will be undertaken. All data will be integrated into a mixed model ANOVA with appropriate post-hoc comparisons by group as appropriate. Analysis will be carried out with the assistance of a qualified biostatistician.

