**Power Calculation and Sample Size:**

The QoR-15 score is a validated outcome metric for quality of recovery (Stark 2013) and is the primary outcome measure for this study. Thus, the QoR was chosen for the power analysis and sample size calculation. Using data from Stark et al 2013, the expected values for the QoR score are average ( $\mu$ ) of 120 and standard deviation ( $\sigma$ ) of 25. We would consider a difference of 8 points to be

clinically significant. Thus, using these values and with an  $\alpha$  of 0.05 and  $\beta$  of 0.8, the calculated sample size is  $n = 154$ . Our study design will allow for a maximum attrition of up to 20% (39 patients), thus we will enroll 200 patients per group (rounding up from 193).

Our group performs approximately 2000 procedures annually (1,973 in FY2016), of which we anticipate 80% will be eligible for this study. Assuming a 50% enrollment rate, it is reasonable to project completion of enrollment in 6 months. Notably, the enrollment rate amongst eligible patients for our completed study on narcotic use after minor hand surgery was greater than 95%. However, this study does require more patient engagement, and so a more conservative estimate has been used. The video length as well as the length and complexity of the diary and surveys are being minimized. Patients will be contacted by phone (with permission) as well as have contact at their follow-up appointment(s) to assist with completion and return of materials. Self-addressed stamped return envelopes will be provided when the patient fails to bring study materials to the first post-operative visit.

Statistical review was conducted by: [name] (name of statistician)  
Carilion (Department/Institution of statistician)

If no statistical review was done, explain why:

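### Control patients can reach the pain-management videos on the institution's YouTube channel, which can dilute the QoR-15 difference, and the protocol does not describe recording which videos each patient watched

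*Protocol*

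**What the plan says.** The contrast under test (18. Study Design) is exposure to a pain-management education programme against exposure to a wound-care one. Section 20, item 4 describes two pain videos and one wound-care video. Patients are encouraged to watch on a tablet in clinic. The videos are also assigned to the patient in MyChart through the GetWellNetwork and are "also available for viewing online on the Carilion channel on YouTube". That sentence covers the videos of both arms.

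Item 5 gives every patient a packet with a video web address. Only the pain arm also receives the Recovery Diary. Item 6 invites patients, without distinguishing arms, to view on the GetWellNetwork and on YouTube.

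Viewing is measured in three ways. One is patient report, which is the version meant for analysis. The Study Abstract describes it as a final-day question on how many times the videos were viewed. The second is GetWellNetwork/MyChart data. The third, in section 21, is "counting Youtube hits".

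The power section sets an 8-point difference in QoR-15 as the target, with SD 25, and allows for "maximum attrition of up to 20% (39 patients), thus we will enroll 200 patients per group (rounding up from 193"). It makes no allowance for control patients seeing the intervention.

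**The concern.** The arms differ by what patients watch and, in the pain arm, by the Recovery Diary. MyChart assignment is made patient by patient and so can keep the videos apart. The YouTube route does not pass through it. Control patients are sent to a platform where, on the text, the pain videos sit on the same channel as their own. They are about to have surgery, and the Background section reports that post-surgical pain is patients' most prominent concern beforehand. The protocol states no restricted link and no request to controls to keep to their own video.

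If some controls watch the pain videos before completing the day 2 QoR-15, the expected difference shrinks below the 8 points the trial is sized for. If viewing is recorded only as a count, the investigators may be unable to say how far this happened. A small difference would then be harder to read.

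**Working it through.** **Inputs.** From Power Calculation and Sample Size: difference 8, SD 25, alpha 0.05, stated 0.8 (printed as beta, read here as power), 154 per group, 20% attrition, 200 enrolled per group. A two-sided test is assumed because it reproduces the stated size. The cross-viewing rate c is not in the documents, so a range is shown.

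**Reproducing the plan's figure.**
- n per group = 2 × [25 × (1.960 + 0.842) / 8]² = 153.3, rounded up to 154. This agrees with the protocol.
- 154 / 0.80 = 192.5, rounded up to 193, then to 200. This also agrees.
- The reserve is therefore only the step from 193 to 200. At 20% attrition, 200 × 0.80 = 160 completers per group.

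**Dilution.** If a share c of controls watches the pain videos and gains the full effect, the expected difference is 8 × (1 − c). Power is that of a two-sided two-sample t-test with noncentrality 8(1 − c) / [25 × √(2/n)]. For n = 160 and c = 0 this is 8 / 2.795 = 2.862, giving 81.4%.

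| Cross-viewing c | Expected difference | Power, 160 per group | Power, 200 per group |
|---|---|---|---|
| 0% | 8.0 | 81.4% | 89.1% |
| 5% | 7.6 | 77.4% | 85.8% |
| 10% | 7.2 | 72.8% | 81.9% |
| 20% | 6.4 | 62.7% | 72.4% |

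**Break-even.** With 160 per group, 80% power needs a true difference of 7.85, so it is lost at c = 1 − 7.85/8, about 2%. With 200 per group (no attrition) it needs 7.02, so it is lost at about 12%.

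**Partial effect.** If a control viewer gains only half the effect, the difference is 8 × (1 − c/2). With 160 per group, power is then 77.4% at 10% cross-viewing and 72.8% at 20%.

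**Cost of absorbing it by sample size.** At c = 10%, n = 2 × [25 × 2.802 / 7.2]² = 189.3, rounded up to 190 completers, and 190 / 0.80 = 237.5, so 238 enrolled per group against 200 planned.

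**The case against.** The protocol does not say whether the YouTube items are listed or unlisted. A web address in an arm-specific packet would fit a direct link to one video. That stands: the text supports that controls can reach the videos, not that they will.

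A reader might infer from section 19, where "the goal of the videos is to have them available" for general patient viewing, that the videos are open to everyone during enrolment. That sentence explains why eligibility is broad and says nothing about access during the trial.

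A reader might also infer that contamination goes unmeasured and that a null result could not be interpreted. Neither follows. Patient report is the measure meant for analysis, and the diary form is not shown, so it may ask video by video. The day 7 knowledge quiz, also not shown, might indirectly indicate whether the education separated the arms. What stands is narrower: the protocol as written describes a count, and no link from YouTube hits to patient or arm.

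Several features limit the size. Viewing starts on a tablet in clinic, the recruitment script does not mention pain, only viewing before the day 2 questionnaire can affect the primary outcome, and controls never receive the Recovery Diary. These make the full-effect model a ceiling. They do not close the route.

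**Conclusion.** The point holds as a design weakness with a plausible route and an unknown rate. The protocol places both arms' videos on one channel and sends both arms online, without stating arm-specific access or describing a record of which videos were watched. This can dilute the QoR-15 comparison; the documents do not show that it will.

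The relevant size is the one at 160 completers per group: a loss of about 4, 9 and 19 percentage points of power at 5%, 10% and 20% cross-viewing. These are upper bounds, provided a control viewer gains no more than the 8 points assumed for the pain arm. If attrition is well below 20%, the reserve is larger, and with none at all 80% power holds to about 12%. The sample-size arithmetic itself is correct.

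Planning to use reported viewing in the analysis does not remove the problem. Viewing is chosen by the patient, so a comparison by viewing is no longer the randomised one.

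**What to change.** This is a cheap improvement, to be settled before enrolment.

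- Until the last patient's 7-day follow-up ends, deliver the videos only through the per-patient MyChart/GetWellNetwork assignment or through unlisted, arm-specific links. If the YouTube items are already unlisted, say so in section 20.
- In both diary versions, ask on day 7 which of the three videos were watched and how often.
- State that the primary QoR-15 comparison is made as randomised, with cross-viewing reported descriptively by arm.

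The cost is a hosting setting and one diary item. Randomisation, care and sample size are unchanged. General release on the channel is delayed, and patients without MyChart need the direct link. The 1-year outcomes are not protected once the videos are released.

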## 7. Data Storage, Data Entry and Statistical Analysis

Paper copies of study materials containing confidential patient information will be stored in locked boxes in the nursing station and in locked drawers in locked areas of the clinic/physician offices. Electronic copies of study materials/collection tools containing patient identifiers/confidential information will be stored on the Carilion S drive or on REDCAP as appropriate. All paper and electronic copies will be retained for 7 years and destroyed according to Carilion accepted research procedure.

A working binder will be maintained for logistical purposes to track and coordinate enrollment, follow-up phone calls and visits, and collection of study materials. The binder will list subject number, name, phone number, dates of surgery and visits, and have columns to track progress through the study protocol. It will be maintained in a locked drawer in a locked office.

Data Entry will be carried out by the investigators.

Statistical analysis will be carried out with assistance of a Carilion Clinic biostatistician. Statistical analysis will include description of the study population and comparison of study groups based on demographic variables. This will include age, surgical site (hand, wrist, forearm/elbow, humerus/shoulder), and type of anesthesia (general vs. local) as these have been shown to affect post-operative narcotic use. Analysis regarding the effect of age, gender, and surgery and medication related variables on the outcome measures will also be carried out. Primary and secondary outcome measures will be

- a. QoR-15 scores (primary outcome),
- b. PROMIS scores,
- c. number of narcotic pills used,
- d. daily pain level (by 0-10 rating scale),

- e. patient-reported satisfaction and feeling of control (4 point rating scale),
- f. number of pain-related calls/visits to a healthcare provider
- g. use of non-narcotic adjunct pain relief medications and modalities,
- h. incidence of high risk activities (combining narcotics with muscle relaxants/sedatives/alcohol, etc.; combining prn NSAIDs with regularly dosed prescription NSAIDs, exceeding daily recommended doses)
- i. incidence of side effects and adverse events,
- j. demonstrated patient knowledge as measured by score on the follow-up quiz, and
- k. prevalence of chronic pain, long term narcotic and non-narcotic pain medication use. .

Analysis regarding the effect of age, gender, and surgery and medication related variables on the outcome measures will also be carried out.

**How this study differs from the usual care a patient will receive:**

Patient education regarding post-operative pain management is usually conducted in an ad-hoc case-by-case basis by the physician or representative that enrolls a patient for surgery. Review of medication for discharge by the nurse at the surgery facility and written post-operative instructions which includes some discussion of post-operative pain control are formalized and a routine part of patient care. This study differs from standard care through the addition of a standardized pre-operative education program in the form of the Pain Management Video series and Recovery Diary to care of the intervention group, and the addition of the Wound Healing Video to the control group. No part of the normal patient care will be removed as part of this study.

**21. Data Collection:** Attach a copy of your data collection tool or spreadsheet listing exactly what data is to be gathered during this research study. Describe below the data collection methods and how data be compiled for assessment.

Data to be collected:

**Patient Demographic Data:**

Name

EMPI

CSN

MRN

Contact phone number

Age

Gender

Pre-existing pain medication use (opioids, acetaminophen, NSAIDS, Lyrica, Neurontin)

Patient race, ethnicity, education level

**Data Related to Surgery:**

Date of Surgery  
Surgical Procedure(s) and anatomic location  
Patient weight  
Anesthetic Type  
Pain Medication Prescribed

**Outcome Measure Data:**

1. QoR-15 scores (primary outcome),
2. Selected short form PROMIS questionnaires,
3. number of narcotic pills used,
4. daily pain level (by 0-10 rating scale) for days 0-7,
5. patient-reported satisfaction and feeling of control (10 point rating scale),
6. calls/visits to a health care provider for pain or related concerns
7. use of non-narcotic adjunct pain relief medications and modalities,
8. incidence of side effects and adverse events
9. reported frequency of noting pain medication dose times,
10. demonstrated patient knowledge as measured by score on the follow-up quiz, and prevalence of chronic pain, long term narcotic and non-narcotic pain medication use.

Data will be collected by chart review (for demographic data and data pertaining to the surgery, anaesthetic, and initial narcotic prescription), physician and patient reporting, and by patient diary/surveys (which will be completed by the patient at home and returned at the follow-up visit or by mail). Follow-up phone calls will act as a reminder to help encourage completion of the study. Information regarding how many times a video was viewed will be collected by patient questionnaire (measured outcome to be used in analysis), reviewing Mychart data, and counting Youtube hits.

22. **Statistical Analysis:** State how qualitative and/or quantitative data will be analyzed. This must include a statement from a statistician that there is sufficient power to determine the primary study outcome or objective. Other outcomes may be listed as secondary and descriptive. If this is a proof of concept or feasibility study that includes limited efficacy testing, there must be a statistician statement that the appropriate design is in place to determine whether an intervention should be recommended for broader efficacy testing. If a study is meant to be solely descriptive, then results apply only to the sample being studied and conclusions cannot be drawn about the larger population; therefore, the primary outcome or objective must be limited in scope.

Standard descriptive statistics will be undertaken. All data will be integrated into a mixed model ANOVA with appropriate post-hoc comparisons by group as appropriate. Analysis will be carried out with the assistance of a qualified biostatistician.

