### SECTION III: STUDY PROTOCOL

15. **Study Abstract:** Provide a brief, non-technical summary of the study, including study purpose and methods.

The purpose of this study is to quantify the impact of a formalized pain management education program on the outcome and experience of patients undergoing outpatient, upper extremity, orthopedic surgery. Outcome measures include the validated Quality of Recovery-15 patient survey and PROMIS survey (selected short forms evaluating pain and medication side effects), as well as measures of patient behavior (amount of pain medication used, number of calls/visits to a medical provider for pain-related concerns), pain levels (1-10 scale), reported side effects, and patient knowledge as measured on a follow-up questionnaire. It is the premise of this study that patient education regarding perioperative pain management could benefit patients in several ways:

- 1) empowering patients to make informed decisions regarding the pain medications and modalities they choose,
- 2) reducing the incidence and severity of pain medication related side effects or complications,
- 3) improving post-operative pain control,
- 4) improving patient satisfaction, and
- 5) reducing the use of narcotic.

Four hundred (400) adult patients undergoing elective outpatient, upper extremity, orthopedic surgeries will be recruited by the surgeon-investigators. Patients will be randomized to view one of two educational programs: 1) a 2-video series regarding post-operative pain management or 2) a video regarding wound care and activity. Randomization will be stratified based on initial narcotic prescription size, which has been shown to influence narcotic use, and baseline pain medication use.

These patients will be encouraged to review the video online in the week before surgery. An intake enrollment form will be completed by an investigator using demographic information available in the chart.

Participants in both arms will complete their Patient Education Study Diary daily, for 7 days following their surgery. There are two versions of this diary: the Wound Education Version asks patients to report daily pain medication use. The Pain Education Version does not include this section as patients in the pain management arm of the study record this information in their Recovery Diary.

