The surgeon will inform the designated enrollment investigator (verbally) of the anticipated prescription class for use in randomization. The designated enrollment investigator will send the surgeon a staff message in EPIC to document that number for reference on the day of surgery.

Patients who agree to participate in the study will sign the consent form. The designated enrollment investigator will keep track of all patients who are consented for surgery but do not enroll in the study, collecting only the number of such patients and their reason for not entering the study (patient declines or which eligibility criterion is not met). No identifying data or other demographic data will be collected from patients who do not consent to enter the study. This information will be recorded in REDCap.

2. Randomization - < 1 minute

They will then be randomized to a study group using a REDCap stratified randomization protocol.

Randomization will be stratified by anticipated post-operative prescription (none, tramadol, 10 narcotic pills, 20 narcotic pills, 30 narcotic pills, >30 narcotic pills). Other factors that will be controlled for through randomization include:

1)

The surgeon and other treating providers will be blinded as to the randomization of the patient. In some cases, the patient may initiate a discussion with the surgeon which necessarily reveals the randomization – this is necessary to avoid interference with physician-patient communication (avoiding negatively impacting patient care) and will be considered acceptable for this study.

3. Data collection – enrollment phase – 10 minutes

An enrollment form is completed by the designated enrollment investigator based on patient interview and/or chart review at the time of enrollment.

At the pre-operative visit prior to video viewing, patients will complete, using REDCap online with the assistance of an investigator, the following:

- I. Quality of Recovery 15 (2.5 minutes)
- II. PROMIS short forms in the following domains: (approximately 6 minutes)
  - a. Physical Health – Gastrointestinal - Belly Pain 5a
  - b. Physical Health – Gastrointestinal – Nausea and Vomiting 4a
  - c. Mental Health – Cognitive Function 4a
  - d. Sleep Disturbance 4a
  - e. Pain Intensity 3a
  - f. Pain Interference 4a
- 4. Educational Intervention (experimental): (6-12 minute video, depending on randomization)
  - 1) Pain Management Education (Intervention)

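### Cheap improvement: name an ANCOVA of POD 2 QoR-15 on baseline QoR-15 and randomisation stratum as the primary test, in place of an unspecified mixed model ANOVA

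*Protocol*

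**What the plan says.** Protocol, Section III, item 17 sets the primary outcome, "QoR-15 scores (post-operative day" 2. Item 20, step 3 collects the same instrument at baseline: "At the pre-operative visit prior to video viewing, patients will complete" a set of forms headed by "Quality of Recovery 15 (2.5 minutes").

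Item 20, step 2 describes the allocation: "Randomization will be stratified by anticipated post-operative prescription (none, tramadol, 10 narcotic pills, 20 narcotic pills, 30 narcotic pills, >30 narcotic pills"). A list of further controlled factors follows, but its content is not readable in this copy. The abstract (item 15) describes the strata differently: "Randomization will be stratified based on initial narcotic prescription size, which has been shown to influence narcotic use, and baseline pain medication use". Item 21 records "Pre-existing pain medication use (opioids, acetaminophen, NSAIDS, Lyrica, Neurontin") and, separately, under the surgical data, "Pain Medication Prescribed".

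Item 22 states the analysis: "All data will be integrated into a mixed model ANOVA with appropriate post-hoc comparisons by group as appropriate". It names no covariate, time point or primary contrast. Item 20, step 7 plans a further analysis of how age, gender, surgery and medication variables affect the outcomes. It is worded as an addition and does not mention baseline QoR-15.

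The sample size under item 22 uses SD 25, a difference of 8, alpha 0.05 and a value of 0.8 labelled β. It gives 154 per group, and 200 per group enrolled after allowing for 20% attrition.

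**The concern.** A baseline score on the primary outcome's own scale is usually the most useful covariate available, and randomisation strata are normally carried into the model. Here both are collected, but the stated model assigns neither a role in the primary comparison. If they predict POD 2 QoR-15, leaving them out gives a wider confidence interval than the data allow.

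The sentence also leaves the primary contrast open. Putting all data into a mixed model ANOVA could mean an unadjusted POD 2 comparison. It could also mean a model with the two QoR-15 scores as repeated measures, tested by a group-by-time interaction. These tests differ in power, and only the first matches the sample size calculation.

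**Working it through.** **Inputs.** Difference 8 and SD 25 (item 22, power calculation); 154 evaluable per group (same place); 160 per group if 200 are enrolled and 20% are lost (200 × 0.8). The baseline-to-POD 2 correlation r is not in the document, so it is an assumption, shown from 0 to 0.7.

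**Step 1, the plan's own figure.** n = 2 × (1.960 + 0.842)² × 25² / 8² = 153.3, so 154 per group. Then 154 / 0.8 = 192.5, so 193, rounded up to 200. Both figures reproduce as a two-sided, unadjusted, single-time-point comparison (a one-sided test would need 121). The 0.8 labelled β is therefore power.

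**Step 2, formulas.** All powers are from the noncentral t distribution, two-sided 0.05.
- Unadjusted POD 2: standardised effect 8/25 = 0.32, df = 2n − 2.
- ANCOVA with k covariate df: effect 8 / (25√(1 − r²)) × √(1 − k/(2n − 2)), df = 2n − 2 − k. Here k = 6 is baseline (1) plus six prescription classes (5); k = 7 adds a yes/no baseline-medication factor; k = 11 adds instead the five medication groups in item 21.
- Group-by-time test of the two QoR-15 scores, equal SDs: effect 8 / (25√(2(1 − r))), df = 2n − 2.

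**Step 3, power at 154 per group.**

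| r | Unadjusted POD 2 | ANCOVA, k = 6 | ANCOVA, k = 11 | Group-by-time |
|---|---|---|---|---|
| 0.2 | 79.9% | 80.7% | 80.1% | 60% |
| 0.3 | 79.9% | 82.8% | 82.1% | 66% |
| 0.5 | 79.9% | 89.3% | 88.7% | 80% |
| 0.7 | 79.9% | 97.3% | 97.0% | 95% |

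A simulation of 10,000 trials per setting with k = 6 and uninformative classes gave 79.4%, 80.5%, 82.6% and 89.2% at r = 0, 0.2, 0.3 and 0.5. The formula gives 79.1%, 80.7%, 82.8% and 89.3%.

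**Step 4, cost if the covariates are useless (r = 0).** Power is 79.1% (k = 6), 79.0% (k = 7) or 78.5% (k = 11) against 79.9%, a loss of about 0.8 to 1.5 points. Adjustment breaks even at r = 0.14, 0.15 and 0.19, that is, when the covariates jointly explain 2.0%, 2.3% and 3.6% of POD 2 variance.

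**Step 5, precision.** The 95% CI half-width, t × 25√(1 − r²) × √(2/154), is 5.6 points unadjusted, 5.3 at r = 0.3 and 4.9 at r = 0.5, before the small covariate cost.

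**Step 6, at 160 per group.** Unadjusted power is 81.4%; ANCOVA with k = 6 gives 82%, 84%, 90% and 98% at r = 0.2, 0.3, 0.5 and 0.7.

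**The case against.** The strongest objection is one of scope. Covariates of the primary model are ordinary SAP content, a SAP may exist, and one sentence in an ethics application lists no model terms at all. This stands in part: the document does not exclude adjustment, and the planned look at medication variables may cover prescription class. But the protocol does name a model, and a more suitable one can be built from data it already collects.

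Second, the gain depends on a correlation the document does not give. At r = 0.2 it is about 1 point, and below about 0.14 to 0.19 adjustment loses slightly. This stands, so the change is cheap but not free.

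Third, a reader might infer that the primary result rests on a group-by-time interaction and is therefore underpowered. The document does not say so. It fixes POD 2 as the time point and names no contrast. Even on that reading, power reaches 80% at r = 0.5 and 95% at r = 0.7, where ANCOVA's lead is only about 2 points.

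Fourth, item 20 asks for steps in chronological order and lists the baseline forms (step 3) after randomisation (step 2), with an investigator assisting. A self-report made once allocation is known is a weaker covariate. This stands as a condition on the fix. It does not show that patients will in fact know their allocation when they answer.

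**Conclusion.** The point holds as an efficiency improvement. Neither the pre-video QoR-15 nor the randomisation stratum has a stated covariate role in the primary POD 2 comparison, and an ANCOVA giving them one has the same target and needs no more patients. At 154 per group with 6 covariate df, the gain over the unadjusted test is about 1, 3, 9 and 17 points of power at r = 0.2, 0.3, 0.5 and 0.7. ANCOVA also exceeds the group-by-time test throughout that range. The figures assume a true difference of 8, a POD 2 SD of 25, equal SDs at the two times for the interaction, and an r that has to be assumed.

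It would go too far to conclude that the analysis is invalid or the sample size wrong. The unadjusted POD 2 test is valid and 154 per group is the right number for it. Nor can one conclude that adjustment is planned nowhere, since the SAP is not at hand. The unreadable list of further factors in step 2 is no evidence of an error in the plan.

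**What to change.** In item 22, for the primary test:
- Fit an ANCOVA of POD 2 QoR-15 on randomised group, pre-operative QoR-15 and the anticipated prescription class recorded before randomisation. Do not use the prescription later issued, which is a post-randomisation variable.
- Add baseline pain medication use only if it was actually a stratification factor. Items 15 and 20 must be reconciled on this first.
- State a rule for pooling sparse prescription classes.
- Report the group coefficient with its two-sided 95% CI, and say that this is the primary contrast. The mixed model can remain for the repeated daily measures.

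In item 20, have the baseline QoR-15 completed before allocation is generated, or at least before it is disclosed to the patient and the assisting investigator.

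Keep 154 evaluable and 200 enrolled per group. As a minor correction, relabel the β value of 0.8 as power 0.80 (β = 0.20); n does not change.

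The cost is a paragraph of analysis wording, one reconciliation and a stated order of two enrolment steps. It needs no new data and no extra patients, and risks at most about 1.5 points of power if the covariates prove uninformative.
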